KPS - Karnofsky Performance Status
PSCC – patient satisfaction with cancer care scale
CAT – communication assessment tool

Study Summary

Title	TELEPORT Study: A Pilot Feasibility Trial Examining The Use of Telehealth in Post Radiation Therapy Visits
Short Title	TELEPORT Study: Telehealth in Radiation Oncology
Protocol Number	15D.580
Phase	single arm pilot study
Methodology/Study Design	Any malignancy or benign condition treated with radiation single arm feasibility study
Study Duration	24 months for enrollment; 32 months for study duration
Study Center(s)	Single-center
Objectives	
Primary objective:
 
 - to investigate the feasibility of conducting a future phase 2 randomized study comparing telehealth and in person visits for patients returning for a post-radiation treatment visit 
Secondary objectives:
 
 - To examine patient satisfaction with a telehealth visit - To examine patient assessment of physician communication during a telehealth - To examine patient distrust in the healthcare system following a telehealth visit - To examine physician ability to perform a patient assessment during a telehealth visit - To examine physician perceptions of telehealth visits - To examine monetary and time cost to patients for telehealth visits - To calculate clinic savings derived from telehealth visits
Number of Subjects	65
Diagnosis and Main Inclusion Criteria	Patients receiving RT for any indication
Study Therapy,	Telehealth visit for the first post treatment follow up

Dose, Route, Regimen	
Duration of administration and follow-up	Follow up visit 3-8 weeks after completion of radiation treatment
Reference therapy	Standard in person office visit for first post treatment follow up
Statistical Methodology	
Schema	
Subject Signs Consent
 
↓
 
Eligibility is checked; demographics obtained
 
↓
 
Subject registered to Jeff Trial Data base
 
↓
 
At completion of radiation treatment, subject is provided with a date and time for post-treatment follow up
 
↓
 
Subject has post-treatment follow up as a telehealth visit
 
↓
 
Both treating physician and patient are emailed links to respective surveys immediately following visit
 
↓
 
Subject is emailed an online reminder week after completion of follow-up visit and has until 4 weeks from the date of the visit to complete

1.0 INTRODUCTION

This document is a protocol for a human research study. This study is to be conducted according to US and international standards of Good Clinical Practice (FDA Title 21 part 312 and International Conference on Harmonization guidelines), applicable government regulations and Institutional research policies and procedures.

1.1 Specific Aims and Hypothesis

The aim of the study is to determine the feasibility of conducting a future randomized trial comparing virtual telehealth visits and in person office visits for post treatment radiation follow up visits. Due to the length of cancer treatment, many oncology patients have had a long interruption of their normal daily lives, including leave of absences from work and additional, non-treatment office visits, contribute to further disruption of patients' lives when they are just beginning to resume their normal activities. After radiation therapy is complete however, patients may have side effects that warrant evaluation and therefore a post-radiation office visit has become standard for all patients who have received radiation. Minimizing the direct impact of this visit on patients' lives may have a positive impact on their post-treatment quality of life. One method to do so may involve a virtual office visit, which can be performed in the comfort of a patient's home or even in the workplace. This would decrease their time traveling to the doctor's appointment and waiting time in the waiting room as well as potentially decreasing cost to the patient. At this time however, it is unknown if a virtual visit would be sufficient for both the patient and the doctor, in terms of satisfaction and effectiveness of the visit.

In this proposal, we intend to investigate the feasibility of conducting a future randomized clinical trial comparing a telehealth and an in person office post radiation treatment visit. In addition we intend to examine patient and physician attitudes towards telehealth visits as well as physician effectiveness and will assess temporal and monetary costs of the visit for the patients.

We hypothesize we will be able to enroll enough patients in this study to justify a future randomized clinical trial comparing virtual post-radiation evaluations and in person visits. We hypothesize virtual visits will be satisfactory in terms of patient satisfaction, perception of physician communication and healthcare distrust. We further hypothesize that monetary cost, and time expenditure for patients will be decreased for telehealth visits as compared to theoretically calculated costs of in person office visits.

Aim 1: To determine the feasibility of conducting a future randomized trial comparing telehealth and in person visits.

Aim 2: To determine the patient and physician satisfaction as well as clinical effectiveness of telehealth visit in radiation oncology clinics as determined by patient and physician assessment

Aim 3: to determine whether the monetary and time costs associated with telehealth visits are decreased compared to an in person visit

1.2 Background and Rationale

Telemedicine refers to the use of telecommunications technology to deliver health care services to individuals at some distance from the provider (Currell, 2000). Driven by rapid advancements in technology, interest has steadily grown in the use of telemedicine, which has the potential to lower health care costs and improve patient access to care (Currell, 2000; Mair and Whitten, 2000).

Routine follow up care after primary cancer treatment is a promising application of telemedicine. Objectives of follow-up include management of complications from treatment, detection of recurrence, and provision of psychological support and information to the patient (Ataman, 2004; van Hezewijk, 2011). With increasing demand on outpatient services and limited resources, effectiveness of traditional follow-up care at accomplishing these objectives has come under scrutiny (James, 1994; Brada, 1995; Teagle, 2014).

In a variety of different cancers, including breast, colorectal, and testicular, physical examination has not been shown to significantly contribute to the detection of recurrence (Jeffery, 2007; Montgomery, 2007; Cunniffe, 2012). Furthermore, a number of studies have shown that telephone follow-up can be as effective as face-to-face visits at addressing the psycho-social effects of disease and treatment (Gotay, 1998; Beaver, 2010; Marcus, 2010). Nurses who conducted telephone follow-up for early stage breast cancer patients expressed confidence in their ability to deliver care through telemedicine platforms (Beaver, 2010).

Feasibility and acceptability of remote follow-up after treatment has been shown in high grade glioma, breast, prostate, bladder, endometrial, and colorectal cancers (Sardell, 2000; Faithfull, 2001; Shaida, 2007; Beaver, 2009; Kimman, 2010; Smits, 2015). In a randomized trial, Beaver et al. found that breast cancer patients who received follow up through the telephone were no more anxious

despite foregoing physical examination. Patients reported higher levels of satisfaction with telephone follow-up compared to traditional outpatient services with no impairment in the detection of recurrence. Patients cite convenience, reduced travel and wait times, and lower cost as reasons for their preference for remote follow-up (Mair and Whitten, 2000; Beaver, 2010). In another study, Shaïda et al. examined patient satisfaction with nurse-led telephone follow-up of patients with prostate cancer. They found no significant differences in general satisfaction or perception of professional care between telephone and outpatient consultations. However patients who received telephone consultations were less satisfied in terms of depth of relationship with provider and perceived time of visit, perhaps suggesting some limitations in the use of technology to connect with patients.

While evidence is promising, the majority of studies examining telemedicine in follow-up care are not randomized, have small patient numbers and do not use validated tools to assess patient satisfaction. Also, no studies have examined the role of telemedicine in a radiation oncology setting (Dickinson, 2014). Our study aims to confirm patient and physician satisfaction with remote follow-up care using validated tools. We aim to show the acceptability of telemedicine follow-up for patients who have undergone radiotherapy, particularly focusing on the first visit following completion of treatment.

1.3 Study Therapy

Telemedicine refers to the use of telecommunications technology to deliver health care services to individuals at some distance from the provider. It has become an increasingly popular option across various medical specialties, with several studies demonstrating its potential clinical effectiveness. Earlier this year, Thomas Jefferson University Hospital launched an institution-wide TH program to use Telehealth to better connect with patients and their families. Applications have included, but are not limited to, virtual rounds, remote consults, and emergent visits. Training programs for providers, including a program for a Telehealth Coordinator, are being developed by the NACT education working group.

Through the new Telehealth service provided by TJUH, patients are able to connect with TJUH doctors through a smartphone, tablet or computer to receive real-time care, such as on demand visits, scheduled online visits and remote second opinions, from any location convenient to them.

In this trial, patients will receive their first post radiation treatment follow up as a virtual visit using Telehealth. During the visit, the patients will use the application from their own home or any other off-campus location that is convenient for them.

1.4 Clinical Data to Date

Several studies have examined patient perceptions of remote health care delivery. In a 2009 multicenter study from the UK, women with breast cancer with low to moderate risk of recurrence were randomized to telephone or hospital follow up after completion of treatment. Patients randomized to the telephone follow up receive phone calls from breast care nurses at regular intervals as per hospital policy. Patients in the hospital follow up group went for in person hospital follow up visits as per hospital policy. The study measured patient psychological morbidity, information needs, patients' satisfaction and time to recurrence. Participants' satisfaction with information received and with dealing with patient concerns was improved in the telephone group as compared to the hospital group (table 1 and 2). Patient anxiety was comparable in the two groups (figure 1).

Level of satisfaction	Hospital	Telephone	Between groups comparison P value	
			All categories*	First 4 categories
Start of trial				
Very satisfied	79 (46)	78 (45)	0.671	$X^2_{trend}=0.31, 0.576$
Satisfied	67 (39)	71 (41)		
Not very satisfied	4 (2)	8 (5)		
Very unsatisfied	1 (1)	0 (0.0)		
Did not receive information	10 (6)	6 (4)		
Did not need information	10 (6)	10 (6)		
Overall	171 (100)	173 (100)		
Middle of trial				
Very satisfied	57 (49)	110 (80)	<0.001	$X^2_{trend}=19.07, <0.001$
Satisfied	41 (35)	22 (16)		
Not very satisfied	7 (8)	3 (2)		
Very unsatisfied	3 (3)	1 (1)		
Did not receive information	4 (3)	0 (0)		
Did not need information	4 (3)	1 (1)		
Overall	116 (100)	137 (100)		
End of trial				
Very satisfied	78 (55)	121 (80)	<0.001	$X^2_{trend}=14.33, <0.001$
Satisfied	47 (33)	25 (16)		
Not very satisfied	8 (6)	3 (2)		
Very unsatisfied	1 (1)	1 (1)		
Did not receive information	7 (5)	0 (0)		
Did not need information	1 (1)	2 (1)		
Overall	142 (100)	152 (100)		

Table 1: Satisfaction with information received by randomized group. Numbers are percent of women

Level of satisfaction	Hospital	Telephone	χ^2_{trend} , P value
Start of trial			
Very helpful	44 (48)	44 (52)	0.69, 0.405
Helpful	36 (39)	31 (37)	
Not very helpful	10 (11)	9 (11)	
Very unhelpful	2 (2)	0 (0)	
Overall	92 (100)	84 (100)	—
Middle of trial			
Very helpful	28 (44)	80 (88)	28.27, <0.001
Helpful	26 (41)	9 (10)	
Not very helpful	9 (14)	1 (1)	
Very unhelpful	1 (2)	1 (1)	
Overall	64 (100)	91 (100)	—
End of trial			
Very helpful	42 (63)	84 (84)	10.35, 0.001
Helpful	15 (22)	13 (13)	
Not very helpful	10 (15)	2 (2)	
Very unhelpful	0 (0)	1 (1)	
Overall	67 (100)	100 (100)	—

Table 2: helpfulness in dealing with concerns at appointment by randomized group. Numbers are percent of women

[figure not shown]

Figure 1: mean differences with 95% confidence intervals for telephone group minus hospital group for state-trait anxiety inventory

In a 2015 prospective study from the UK, approximately 250 patients with dermatological conditions seen in a general practice setting who would have been subsequently referred to a dermatologist had a teledermatology visit instead. Over the course of 2 years this strategy resulted in an estimated saving of \$18,600. 97% of patients rated themselves as satisfied or very satisfied with the process and 93% felt comfortable with the process.

1.5 Dose Rationale and Risk/Benefits

If during the telehealth visit the treating physician feels he or she is unable to fully assess the patient, or has any concerns, he or she will ask the patient to come in for an in person visit.

2.0 STUDY OBJECTIVES

2.1 Primary Objective:

The primary objective is to examine feasibility of conducting a trial comparing a telehealth visit and an in person office visit

[figure not shown]
2.2 Secondary Objective:

The secondary objectives of this study include to examine patient satisfaction, patient assessment of physician communication during a telehealth visit; to examine patient distrust in the healthcare system following a telehealth visit; to examine physician ability to perform a patient assessment during a telehealth visit; to examine physician perceptions of telehealth visits; to examine monetary and time cost to patients for telehealth visit; to calculate clinic savings derived from telehealth visits.

3.0 STUDY DESIGN

3.1 General Design

This is a single arm pilot feasibility study examining a telehealth visit for the first post radiation treatment visit. Patients will be asked to fill out a questionnaire within a week of the visit. There will be no subsequent follow up per trial. The expected enrollment duration of the study is 24 months. The overall study duration is expected to be 32 months.

3.2 Primary Study Endpoints

The primary endpoint of the study is feasibility (i.e., rate of accrual) of conducting a future randomized clinical trial comparing telehealth and in person visits

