5.0 STUDY DRUG/THERAPY

5.1 Description

Through the new Telehealth service provided by TJUH, patients are able to connect with TJUH doctors through a smartphone, tablet or computer to receive real-time care, such as on demand visits, scheduled online visits and remote second opinions, from any location convenient to them.

In this trial, patients will receive their first post radiation treatment follow up as a virtual visit using Telehealth.

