5.4 Method for Assigning Subjects to Treatment Groups

This is a single arm study

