7.0 STATISTICAL PLAN

7.1 Sample Size Determination

Accrual rate. This pilot study is designed to assess whether the accrual rate at Jefferson will be sufficient for a future noninferiority trial. For that noninferiority trial, we project that we will need to enroll a total of about 180 patients in three years, i.e., a minimum accrual rate of 5 patients per month. The enrollment duration of this pilot study will be 24 months. If the true accrual rate is 6 patients per month (i.e., 72 patients per year), then the pilot study has 83% power to establish that the accrual rate exceeds 5 patients per month (using a 1-sided test for Poisson rate, with alpha 0.05).

Patient satisfaction. The expected sample size of 60 patients will also have >90% power to establish that patient satisfaction will exceed 80%, assuming a true PSCC score of about 90% and a standard deviation of about 5% (using a one-sample t-test with alpha 0.05).

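### Accrual to a single-arm, all-telehealth pilot is compared directly with the 5/month a randomised trial needs, and nothing collected shows how many enrollees would accept random assignment

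*Combined protocol and SAP*

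**What the plan says.** Section 3.2 makes the primary endpoint "feasibility (i.e., rate of accrual) of conducting a future randomized clinical trial" that would compare telehealth with in-person visits. Section 7.1 gives the purpose: "This pilot study is designed to assess whether the accrual rate at Jefferson will be sufficient for a future noninferiority trial". It also gives the yardstick for the future trial: "we will need to enroll a total of about 180 patients in three years, i.e., a minimum accrual rate of 5 patients per month". Section 7.2 then tests the monthly accrual rate.

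The pilot itself does not randomise. Section 3.1 states "This is a single arm pilot feasibility study examining a telehealth visit for the first post radiation treatment visit", section 5.4 repeats "This is a single arm study", and under section 5.1 "patients will receive their first post radiation treatment follow up as a virtual visit using Telehealth". Inclusion criterion 5 in section 4.1 requires willingness to use telehealth; no criterion concerns willingness to be randomised.

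The only other feasibility measure is in section 7.2: the proportion of enrolled subjects lost to follow-up. It is descriptive and has no threshold.

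The screening procedures (6.1), the flowchart (6.1.1) and the case report forms (Appendix II) contain no question on accepting chance assignment or an in-person visit. They describe no count of patients approached or declining, and no record of reasons.

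**The concern.** Consent to a study that guarantees telehealth and consent to a trial that may assign an in-person visit are different decisions. Comparing the first rate with the target for the second assumes, without saying so, that everyone who makes the first decision would also make the other.

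The protocol's own rationale suggests why some might not. Section 1.2 reports that patients prefer remote follow-up for convenience, shorter travel and waiting, and lower cost, and section 1.1 expects telehealth to save patients time and money. The pilot assures that benefit; a randomised trial would withhold it from one arm.

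At stake is the decision the pilot exists to inform. The plan could be followed exactly and still return a positive feasibility result for a randomised trial that would not reach 5/month. Willingness at the time of consent cannot be reliably recovered afterwards, so it has to be recorded prospectively.

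**Working it through.** **Inputs.** From section 7.1: future target 180 patients in 36 months, so 180/36 = 5/month; planned pilot rate 6/month; 24 months of enrolment; one-sided Poisson test, alpha 0.05; null 5/month; stated power 83%. From section 7.2: null 4/month. Assumed, because the documents give no value: *r*, the share of pilot enrollees who would also accept randomisation.

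**1. The plan's own power figure.** Under a rate of 5/month, 24 months gives an expected count of 5 × 24 = 120; under 6/month, 6 × 24 = 144. The smallest count *c* with P(X ≥ c | mean 120) ≤ 0.05 is 139 (exact alpha 0.048). Power is P(X ≥ 139 | mean 144) = 67.3%, so the stated 83% does not reproduce at 24 months. A figure near it appears for 36 months (82.0% exact). This is a separate matter; the point here does not depend on it.

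**2. Share needed at the planned rate.** Randomised accrual = pilot rate × *r*. Setting 6 × *r* = 5 gives *r* = 5/6 = 0.833. A loss of more than one enrollee in six is enough to miss the target.

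**3. Range over the assumed share, at a pilot rate of 6/month.**

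| Assumed *r* | Randomised accrual, 6 × *r* | Months for 180 patients, 180/(6 × *r*) |
|---|---|---|
| 1.0 | 6.0/month | 30 |
| 0.9 | 5.4/month | 33.3 |
| 0.8 | 4.8/month | 37.5 |
| 0.7 | 4.2/month | 42.9 |
| 0.5 | 3.0/month | 60 |

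The target is 36 months. It is met at 90% and missed at 80% and below.

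**4. Share needed at the smallest passing count.**
- Null of 5 (section 7.1): 139/24 = 5.79/month; share needed 5/5.79 = 0.863.
- Null of 4 (section 7.2): expected count 4 × 24 = 96, critical count 113 (exact alpha 0.049); 113/24 = 4.71/month. This is below 5/month even at *r* = 1.

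**5. What the test can see.** At a true 6/month the pilot passes with probability 67% (null 5) or 99.7% (null 4), whatever *r* is. The primary analysis carries no information on *r*.

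**6. Would it help to test the willing rate instead?** With 6/month enrolled and the null of 5 over 24 months, exact power is 67% at *r* = 1, 22% at *r* = 0.9 (5.4/month) and 7.5% at *r* = 0.85 (5.1/month). The last two rates would both meet the target, yet the pilot would usually fail. Willingness is therefore better reported than tested.

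**The case against.** The strongest reply is that a single-arm pilot measuring accrual before a randomised trial is a disclosed and consistently described choice, with no internal contradiction. That stands, and nothing here asks for a randomised pilot.

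Second, the size of any loss is assumed. That also stands: at 90% willing the target is met, and the documents do not show where the true share lies.

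Third, a reader might infer that pilot accrual is an upper bound for randomised accrual, or that the feasibility decision is biased toward a positive result. The documents do not establish either. The pilot is unfunded (section 11.1) and the telehealth service was new (section 1.3), so later recruitment conditions could be better. In-person follow-up is already standard (section 1.1), so the control arm would ask for nothing beyond usual care. Overstatement is the plausible direction, but that is reasoning and not a documented fact.

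Fourth, a reader might take section 7.3 as claiming that all pilot enrollees would join the randomised trial. In context, that sentence explains why withdrawn and lost subjects still count toward accrual. It makes no claim about willingness to be randomised.

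Fifth, loss to follow-up is also summarised with feasibility in mind. True, but it describes what happens after enrolment and cannot answer a question about consent.

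Finally, the conflict between the nulls of 5 and 4 is a firmer defect in this endpoint, because under the null of 4 the pilot can pass below 5/month with no randomisation problem at all. That is so, and it needs its own correction. Resolving it would not supply the missing information on willingness.

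**Conclusion.** The concern holds in a limited form. The plan compares single-arm accrual directly with a randomised trial's requirement and collects nothing that links the two, so a positive result could be returned when the randomised trial would fall short. At the planned 6/month the break-even share is 83%; at the smallest count that rejects 5/month it is 86%.

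These break-even shares follow from the plan's own rates. The 5.4 to 3.0/month range (about 33 to 60 months for 180 patients) rests on assumed shares of 90% to 50%, and on recruitment conditions otherwise staying the same. The documents do not support saying that the randomised trial will fail, or by how much the pilot overstates accrual. This is an improvement the sponsor should make because it is cheap and has to be prospective; it does not invalidate the design.

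Three related items need reconciling separately: the null of 5 in section 7.1 against 4 in section 7.2; the 83% power; and the 65 subjects in the Study Summary and 60 expected in section 7.1 against the 144 implied by 6/month for 24 months.

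**What to change.** Keep the single arm and the formal test on the total accrual rate.

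1. Add one yes/no item to the screening case report form, asked at consent: would the patient have joined if telehealth or an in-person visit had been assigned by chance?
2. Have the staff who already screen keep a log of patients eligible, approached, consented and declined, with reasons for declining. The log would also pick up patients who decline assured telehealth but might accept randomisation.
3. In section 7.2, report descriptively, with confidence intervals, the proportion and monthly rate of enrolled patients who answer yes, beside the total rate and the 5/month target. State that the total rate may overstate randomised accrual.

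The cost is one question, one log and a short descriptive analysis, which is manageable for an unfunded study. The downsides are that stated willingness is hypothetical and that the feasibility picture may look less favourable.
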